2 STUDY OBJECTIVES

2.1 Primary Objective

- Efficacy of AR101 treatment in peanut-allergic subjects aged 1 to < 4 years, assessed by tolerability of specified doses of peanut protein in a DBPCFC

2.2 Secondary Objectives

- Safety and tolerability of study treatment
- Efficacy of AR101, assessed by tolerability of other specified single doses of peanut protein in a DBPCFC
- Maximum severity of allergy symptoms in a DBPCFC

2.3 Exploratory Objectives

- Immunologic changes
- Changes in control of pre-existing atopic disease (asthma, atopic dermatitis)

3 INVESTIGATIONAL PLAN

3.1 Overall Study Design and Plan: Description

This is a phase 3, international, randomized, double-blind, placebo-controlled study of the efficacy and safety of AR101 in peanut-allergic children aged 1 to < 4 years. The study will be conducted at approximately 25 study sites in North America and Europe.

Eligible subjects who develop age-appropriate dose-limiting allergy symptoms after consuming single doses of peanut protein > 3 mg to \leq 300 mg in a screening DBPCFC will be randomly assigned 2:1 to blinded treatment with AR101 or placebo. Randomization will be stratified by geographic region (North America, Europe).

Subjects will begin initial dose escalation under medical supervision at the study site on day 1 with a stepwise dose escalation of study product (up to 4 single doses of 0.5, 1, 1.5, and 3 mg) administered at 20- to 30-minute intervals as tolerated. Subjects who tolerate the 3 mg dose on day 1 will return on day 2 for a single 1 mg dose. Subjects who tolerate the 1 mg dose with no more than mild allergy symptoms that are not dose-limiting will begin the up-dosing period. Subjects who do not tolerate any dose on day 1 or day 2 will discontinue early from the study.

The up-dosing period will be approximately 6 months (maximum 40 weeks), with dose escalation approximately every 2 weeks. Daily doses of study product during up-dosing will be 1, 3, 6, 12, 20, 40, 80, 120, 160, 200, 240, and 300 mg/day. The first dose of study product at each new dose level will be administered under medical supervision at the study site; the remaining doses at each dose level will be administered daily at home as tolerated. Dose adjustments may be allowed. Subjects who tolerate the 300 mg/day dose for 2 weeks within 40 weeks will begin the maintenance period. Subjects unable to tolerate the 300 mg/day dose for 2 weeks within 40 weeks of up-dosing will discontinue early from the study.

Subjects who begin maintenance treatment will continue daily dosing with study product at 300 mg/day for an overall total of approximately 12 months of treatment, with study site visits every 4 weeks. The duration of maintenance treatment may vary from a minimum of 12 weeks to a maximum of 24 weeks depending on the up-dosing interval (24-40 weeks). Dose adjustments may be allowed. After the end of maintenance, subjects will have an exit DBPCFC up to a single highest challenge dose of 2000 mg peanut protein (4043 mg cumulative). The 300 mg daily dose of study product must be tolerated for at least 2 consecutive weeks before having the DBPCFC. Subjects who complete both days of the exit DBPCFC will exit (complete) the study. Study treatment assignment will be unblinded for a subject after all major data queries for the subject are resolved. Eligible subjects will have the option to enroll in an open-label, follow-on study to receive AR101 treatment. If

the follow-on study is not yet available at the study site, blinded study treatment may continue and the visit schedule will be every 4 weeks until the follow-on study is available.

[figure not shown]
At early discontinuation or study exit, subjects with unresolved adverse events or who had GI adverse events of interest (ie, GI adverse events that result in dose interruption > 7 consecutive days or early discontinuation) will have safety follow-up.

An independent, external data and safety monitoring committee (DSMC) will monitor safety on a periodic basis.

In the event of a pandemic (eg, Coronavirus Disease 2019 [COVID-19] pandemic), epidemic, or other emergency not related to the study (eg, natural disaster, act of war or terrorism), restrictions may be issued at the country, state, regional, and/or local level that may affect study conduct, the scientific integrity of the study, or the safety and well-being of study participants and study site staff. When such restrictions and associated challenges (eg, site closures; travel restrictions; quarantines; pandemic- or epidemic related illness in subjects, parents, caregivers, or study site personnel) prevent the conduct of study site visits (ie, onsite) or access to study product for an extended period, changes to certain study procedures will be implemented in accordance with regulatory requirements to ensure subject safety and continued treatment, care, and sponsor oversight as described in [Appendix 3](#).

3.2 Study Schematic

The study schematic is provided in [Figure 1](#).

Figure 1: Study Schematic

- [1] Eligible subjects must have age-appropriate dose-limiting allergy symptoms after consuming single doses of peanut protein > 3 mg to ≤ 300 mg in the screening DBPCFC.
- [2] Subjects with unresolved adverse events or who had gastrointestinal adverse events of interest will have safety follow-up.

DBPCFC, double-blind, placebo-controlled food challenge.

3.3 Blinding

Study treatments and immunology laboratory results obtained after screening will be blinded. All subjects, study site personnel (including investigators), and sponsor staff and its representatives will be blinded to treatment identity, except the designated unblinded person who will access the interactive response system to obtain the randomization order for the peanut protein and placebo challenge days, and prepare the DBPCFC material.

Study treatment assignment will be unblinded for each subject after completion of their exit DBPCFC and after all major data queries for the subject are resolved.

3.4 Study Suspension Criteria

The study will be suspended if any of the following occur:

- A treatment-associated death in a subject receiving AR101 in this study
- Two subjects hospitalized within 6 months of each other for intensive treatment due to AR101-related adverse events

- Three subjects hospitalized for intensive treatment due to AR101-related adverse events
- Greater than 2 cases of AR101-related anaphylaxis resulting in hypotension, neurologic compromise, or mechanical ventilation (modified European Academy of Allergy and Clinical Immunology [EAACI] grade 3 per [Section 8.5](#); clinical assessment per [Section 8.6.1.1](#))

Admission to the hospital for observation only (not for intensive treatment of a serious AR101-related adverse event) will not be considered contributory to the study suspension criteria. The DSMC may also recommend halting the study for any substantial imbalance in adverse events apart from anticipated study product-related allergy symptoms, based on review of the safety data.

In the event of study suspension based on the above criteria, enrollment and dose escalation will be halted. Dosing at the current tolerated dose level will continue unless otherwise directed by the sponsor or by the regulatory authority for a participating country. Study suspension will not be lifted until after the safety data are discussed with regulatory authorities and the regulatory authorities agree with resuming enrollment and dose escalation.

The sponsor may suspend the study in the event of a pandemic, epidemic, or other emergency not related to the study if the resulting restrictions do not permit conduct of the alternate procedures described in [Appendix 3](#). Study suspension will not be lifted until after consideration of individual subjects; study sites; and local, state, regional, and national guidance as applicable; and in accordance with regulatory requirements.

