AR101 was generally well tolerated in the safety population of subjects aged 4 to 17 years (372 AR101, 124 placebo). The safety profile remains consistent with previous findings of hypersensitivity events (allergic reactions), manifesting primarily as mild to moderate gastrointestinal (GI) symptoms in decreasing order of abdominal pain, vomiting, pruritus, upper abdominal pain, cough, throat irritation, oral pruritus, nausea, urticaria, and rhinorrhea that generally decreased in incidence with treatment from up-dosing to maintenance. When adjusted for exposure, the most frequent adverse events and symptoms overall in the AR101 group were throat irritation, oral pruritus abdominal pain, upper abdominal pain, nausea, and oral paresthesia. One event of biopsy-confirmed eosinophilic esophagitis (EoE) was reported. No subject died or had any life-threatening adverse event or symptom, and the incidence of treatment-related severe events for AR101-treated subjects was low (2.4%). The incidence of serious adverse events for AR101-treated subjects was also low (2.2%), including 3 with anaphylactic reaction (1 severe [anaphylaxis] in a subject with high peanut-specific immunoglobulin [Ig] E > 100 kU/L at baseline) and 2 with exacerbation of asthma. All serious adverse events resolved. Systemic allergic reactions (Medical Dictionary for Regulatory Activities [MedDRA] preferred term anaphylactic reaction) were generally mild or moderate severity and resolved rapidly with treatment; 1 event was serious and severe anaphylaxis as just described. Epinephrine was used by 14.0% of AR101-treated subjects and 6.5% of placebo-treated subjects, and the majority of use was for mild or moderate adverse events and symptoms (including systemic allergic reactions) after study

product dosing at home during up-dosing and maintenance. About 10% of subjects discontinued due to adverse events, and most discontinuations were due to GI events during up-dosing. Adverse events associated with accidental food allergen exposure were less common overall in the AR101 group, possibly indicating less vulnerability to peanut exposure over time with treatment. The overall safety profile of AR101 was similar to that observed in the phase 2 studies of AR101 and previous studies of peanut OIT ([Anagnostou, 2014](#); [Yu, 2012](#); [Varshney, 2011](#); [Blumchen, 2010](#); [Hofmann, 2009](#); [Jones, 2009](#)).

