Severity of anaphylaxis will be graded according to the modified EAACI guidelines ([Table 8](#); adapted from [Muraro, 2007](#)). The clinical assessment of anaphylaxis is described in [Section 8.6.1.1](#).

Table 8: Modified EAACI Severity Grading System for Anaphylaxis

Severity Grade	Description	Symptoms
1 – Mild	Involves skin and subcutaneous tissues, gastrointestinal, and/or mild respiratory	Flushing; urticaria; periorbital edema or facial angioedema; mild dyspnea, wheeze, or upper respiratory symptoms; mild abdominal pain and/or emesis
2 – Moderate	Involves mild symptoms and features suggesting moderate respiratory, cardiovascular, or gastrointestinal symptoms	Marked dysphagia, hoarseness, and/or stridor; shortness of breath, wheezing, and retractions; crampy abdominal pain, recurrent vomiting, and/or diarrhea; and/or mild dizziness
3 – Severe	Involves hypoxia, hypotension, or neurologic compromise	Cyanosis or $\text{SpO}_2 \leq 92\%$ at any stage, hypotension [1], confusion, collapse, loss of consciousness, or incontinence

Source: Adapted from [Muraro, 2007](#).[1] Systolic blood pressure: $< 70 \text{ mm Hg}$ in subjects aged 1 month to 1 year, $< (70 \text{ mm Hg} + [2 \times \text{age}])$ in subjects aged > 1 to 10 years.

EAACI, European Academy of Allergy and Clinical Immunology.

Severity of all other adverse events will be graded according to the National Cancer Institute (NCI) Common Terminology Criteria for Adverse Events (CTCAE). CTCAE terms are grouped by system organ class, graded 1 to 5, and have unique clinical descriptions of severity for each adverse event based on the general guideline presented in [Table 9](#).

Table 9: NCI CTCAE Severity Grading System for Adverse Events

Grade 1 Mild	Grade 2 Moderate	Grade 3 Severe	Grade 4 Life-Threatening	Grade 5 Death
Asymptomatic or mild symptoms; clinical or diagnostic observations only; intervention not indicated	Minimal, local, or noninvasive intervention indicated; limiting age-appropriate instrumental activities of daily living	Severe or medically significant but not immediately life-threatening; hospitalization or prolongation of hospitalization indicated; disabling; limiting self-care activities of daily living	Life-threatening consequences; urgent intervention indicated	Death

Source: NCI CTCAE.

NCI CTCAE, National Cancer Institute Common Terminology Criteria for Adverse Events.

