Moderate	
Administer the previous tolerated dose of study product the next day at the study site.
 
 • If no symptoms occur with the reduced dose, continue that dose level for 2 weeks before attempting re-escalation. • If mild symptoms occur at the reduced dose, follow the guidelines for mild symptoms. • If moderate symptoms occur at the reduced dose, give a second reduced dose (1 or 2 dose levels lower) the next day at the study site. 
 – If the second reduced dose is tolerated, continue that dose level for at least 2 weeks before attempting re-escalation. – If mild symptoms occur with the second reduced dose that is assessed as not tolerated, follow the guidelines for mild symptoms. – If moderate symptoms recur at the second reduced dose, discuss early discontinuation with the medical monitor. 
 ▪ If a third reduced dose is considered to be safe after discussion with the medical monitor, give it at the study site under medical supervision. If the dose is assessed as not tolerated, stop study product dosing and discontinue the subject early from the study (Section 5.3). 
In the rare case that a dose with moderate symptoms is assessed as tolerated, follow the guidelines for mild symptoms and provide a brief explanation for the assessment on the case report form.

Severe	
Discuss early discontinuation with the medical monitor. If continuation of study product is considered to be safe, administer a reduced dose at 2 dose levels the next day at the study site under medical supervision. If the reduced dose is tolerated, continue that dose level for at least 2 weeks before attempting re-escalation. If the reduced dose is assessed as not tolerated, stop study product dosing and discontinue the subject early from the study (Section 5.3).

Life-threatening	
Stop study product dosing and discontinue the subject early from the study (Section 5.3).

Assess dose tolerability per [Section 8.6.1.2](#).

[1] Depending on the subject's stage of development, allergy symptoms may be difficult to interpret. Age-appropriate allergy symptoms should be considered when determining the appropriate actions to be taken with study product dosing.

GI, gastrointestinal.

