5 STATISTICAL METHODS

Changes to the statistical methods and data presentations for reporting the study due to any restrictions will be detailed in the statistical analysis plan.

Limits to the prespecified maximum duration of up-dosing and maintenance periods for subjects to meet the criteria of responders at the exit food challenge will continue to apply, with the exception of any duration of time affected by the restrictions as defined by the first and last consecutively affected study visits. For instances of multiple distinct durations of

restriction, the maximum duration of the up-dosing and maintenance periods will be extended by the cumulative sum of these distinct durations of affected study visits.

Subjects who discontinue early from the study for any reason before completing their scheduled exit food challenge, including due to the restrictions, will be counted as nonresponders in an intent-to-treat analysis, and may also be excluded from an alternative sensitivity analysis of the primary and prespecified secondary endpoints as appropriate.

Additional subjects may need to be enrolled to accommodate a potential increase in dropouts, a substantial extension of the up-dosing period, or a substantial delay in completion of exit food challenges. In the event a greater than anticipated number of subjects discontinue early from the study due to the restrictions, the study sample size may be increased by up to 20% without protocol amendment. The sponsor may perform one or more blinded sample size reassessments, potentially in consultation with an external unblinded data and safety monitoring committee, to address any safety concerns associated with an increase in the study sample size.

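### The fourth suspension criterion cites modified EAACI grade 3 but omits hypoxia, so a hypoxia-only, non-ventilated grade 3 case both counts and does not count

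*Combined protocol and SAP*

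**What the plan says.** Section 3.4 sets four mandatory suspension criteria. The fourth is "Greater than 2 cases of AR101-related anaphylaxis resulting in hypotension, neurologic compromise, or mechanical ventilation", followed in parentheses by "modified European Academy of Allergy and Clinical Immunology [EAACI] grade 3 per" Section 8.5, with the clinical assessment referred to Section 8.6.1.1.

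Table 8 in Section 8.5 describes grade 3 as: "Involves hypoxia, hypotension, or neurologic compromise". Its symptom column gives cyanosis or SpO2 of 92% or less, at any stage, among the signs.

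The other three mandatory criteria are a treatment-associated death on AR101, two subjects hospitalized for intensive treatment of AR101-related events within 6 months of each other, and three such subjects at any time. Section 3.4 adds: "Admission to the hospital for observation only (not for intensive treatment of a serious AR101-related adverse event) will not be considered contributory". The DSMC may also recommend a halt for "any substantial imbalance in adverse events apart from anticipated study product-related allergy symptoms".

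Suspension stops enrollment and dose escalation, and it is lifted only after regulators agree.

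**The concern.** The criterion is defined twice in one sentence, once by a list of outcomes and once by a grade, and the two definitions differ in both directions. If the grade governs, the list misstates it. If the list governs, the grade label is wrong.

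The case affected is AR101-related anaphylaxis with SpO2 of 92% or less, or cyanosis, but no hypotension, neurologic compromise or ventilation. It is grade 3 by Table 8 and has none of the features listed in Section 3.4. The trigger fires once the count exceeds 2, so three such cases give opposite instructions depending on which half of the sentence is applied. At stake is whether a mandatory halt of enrollment and dose escalation happens in a trial of children aged 1 to under 4.

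**Working it through.** **Text comparison**

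| Feature | Listed in Section 3.4 | Grade 3 in Table 8 |
|---|---|---|
| Hypotension | yes | yes |
| Neurologic compromise | yes | yes |
| Hypoxia (cyanosis or SpO2 ≤ 92%) | no | yes |
| Mechanical ventilation | yes | no |

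Table 8 joins its features with "or", so hypoxia alone is enough for grade 3. Section 8.6.1.1 gives hypoxemia as an example of respiratory compromise when diagnosing anaphylaxis, but does not limit grade 3 to the Section 3.4 list. Table 4 in Section 5.3 uses the same three features as an example of CoFAR grade 4, so the list does not identify one grade on one scale.

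**Do the other mandatory criteria catch the case?** Only if the child dies or is hospitalized for intensive treatment often enough to meet criterion 2 or 3. Where Table 6 (Section 8.3) illustrates intensive therapy, it says that one or two intramuscular epinephrine injections typically do not qualify. A child who desaturates, receives intramuscular epinephrine and oxygen, recovers and is only observed can be grade 3 and meet no other mandatory criterion. Oxygen saturation is among the vital signs taken after site doses (Table 2, Section 9.4.4), so this route to grade 3 is routinely measured.

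**Size.** The plan gives no operating characteristic for this rule, so there is no figure of its own to reproduce. The following is an illustration.

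Inputs:
- Rate: ARC003 (Section 1.2.2) had 372 AR101 subjects aged 4 to 17; of its systemic allergic reactions, "1 event was serious and severe anaphylaxis as just described". So p = 1/372 = 0.27%, exact (Clopper-Pearson) 95% CI 0.007% to 1.49%.
- AR101 subjects: 88 (Section 10.3). Appendix 3, Section 5 says "the study sample size may be increased by up to 20% without protocol amendment", giving 132 × 1.2 × 2/3 = 105.6, about 106.
- h, the share of grade 3 cases that are hypoxia-only: not in the documents, taken as 25%, 50% and 75%.

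Formulas, with at most one case per subject:
- Table 8 reading: P(X ≥ 3), X ~ Binomial(n, p).
- Listed-features reading: P(Y ≥ 3), Y ~ Binomial(n, p(1 − h)).
- With no ventilated cases Y cannot exceed X, so the readings disagree with probability P(X ≥ 3) − P(Y ≥ 3).

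| n | p | Table 8 | Listed features, h = 25 / 50 / 75% | Readings disagree |
|---|---|---|---|---|
| 88 | 0.27% | 0.18% | 0.08 / 0.02 / 0.003% | 0.10 / 0.16 / 0.18% |
| 106 | 0.27% | 0.30% | 0.14 / 0.04 / 0.006% | 0.17 / 0.26 / 0.30% |
| 88 | 1.49% (upper limit) | 14.4% | 7.6 / 2.8 / 0.4% | 6.8 / 11.6 / 14.0% |
| 106 | 1.49% (upper limit) | 21.0% | 11.6 / 4.5 / 0.7% | 9.4 / 16.5 / 20.3% |

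**The case against.** The strongest reply is that the mismatch is real but has little effect. Three hypoxia-only cases would have to occur, none with hypotension, neurologic signs, ventilation or death, and with too few intensive-treatment hospitalizations to trigger criterion 2 or 3. Criterion 2 fires at two hospitalizations, a lower count than this criterion needs. The calculation assumes no such hospitalizations, so its disagreement figures lean high. The upper-limit figures come from a single event in older subjects combined with assumed shares. The trial also excludes children with previous severe or life-threatening anaphylaxis (Section 4.2).

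Such cases would also be seen. Anaphylaxis and severe adverse events must be reported within 24 hours (Section 8.7.2), the sponsor reviews individual safety reports (Section 8.1), and severe symptoms require a discussion with the medical monitor about discontinuing that child (Table 12). The DSMC carve-out for anticipated allergy symptoms need not cover anaphylaxis with cyanosis, and the DSMC charter, which is not among the documents, may settle how cases are counted. The repeated phrase in Table 4 could mean the list was deliberate and the grade is only a loose cross-reference.

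The points on likelihood and visibility stand, and they lower the priority. None of them gives the trigger one meaning. Reporting and the medical monitor discussion are mandatory, but neither suspends the study; a sponsor or DSMC halt is a matter of judgment. If the list was deliberate, the grade 3 label is the error and still needs removing.

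**Conclusion.** The concern holds. The fourth criterion contradicts the grade it cites, and the protocol does not say which prevails. This is an error of wording in a mandatory safety rule; it does not threaten the efficacy analysis.

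The likely effect is small: about 0.1% to 0.3% at the observed rate, allowing for the permitted 20% increase. The larger upper-limit figures show how little one event establishes about the rate and should not be read as expected impact. All figures assume that the ARC003 rate carries over to ages 1 to under 4, that severe anaphylaxis there corresponds to grade 3 here, one case per subject, no ventilated case, and no hospitalization for intensive treatment. The hypoxia-only shares are assumptions. The text mismatch depends on none of these. The correction should be made, because a mandatory trigger should not depend on which half of a sentence the reader applies.

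**What to change.** Reword the fourth criterion in Section 3.4 to: more than 2 cases of AR101-related anaphylaxis that are modified EAACI grade 3 (hypoxia, hypotension or neurologic compromise; Section 8.5) or that require mechanical ventilation. If hypoxia-only cases are meant to be excluded, keep the present list, remove the grade 3 label and state the exclusion.

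The first option costs some sensitivity if the list was what the sponsor intended: the suspension probability moves from the listed-features values to the Table 8 values above, which is negligible at the observed rate and larger if the true rate is near the upper limit. The edit is one line and needs no new data, visits or subjects, because investigators already grade every anaphylaxis event. If it is classed as a substantial amendment, Section 13.1.1 requires ethics committee and regulatory approval first, so it is best combined with the next amendment. The DSMC charter should use the same definition.
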